7.3.6. Clinical Safety Laboratory Assessments

All protocol required laboratory assessments, as defined in [Table 7](#), must be conducted in accordance with the Laboratory Manual, and Protocol Time and Events Schedule. Laboratory requisition forms must be completed and samples must be clearly labelled with the subject number, protocol number, site/centre number, and visit date. Details for the preparation and shipment of samples will be provided by the laboratory and are detailed in the SRM. Reference ranges for all safety parameters will be provided to the site by the laboratory responsible for the assessments.

If additional non-protocol specified laboratory assessments are performed at the institution's local laboratory and result in a change in subject management or are considered clinically significant by the investigator (e.g., SAE or AE or dose modification) the results must be recorded in the CRF.

Refer to the SRM for appropriate processing and handling of samples to avoid duplicate and/or additional blood draws.

Haematology, clinical chemistry, urinalysis and additional parameters to be tested are listed in [Table 7](#).

Table 7 Protocol Required Clinical Safety Laboratory Assessments

Laboratory Assessments	Parameters			
Haematology	Platelet Count	RBC Indices:	WBC count with Differential:	
	RBC Count	MCV	Neutrophils	
	Hemoglobin	MCH	Lymphocytes	
	Hematocrit		Monocytes	
	Prothrombin Time		Eosinophils	
			Basophils	
Clinical Chemistry ¹	BUN	Potassium	AST (SGOT)	Total and direct bilirubin
	Creatinine	Sodium	ALT (SGPT)	Total Protein
	Glucose	Calcium	Alkaline phosphatase	Albumin
	Phosphate	Bicarbonate		
Routine Urinalysis	
 • Specific gravity • pH, glucose, protein, blood and ketones by dipstick • Microscopic examination (if blood or protein in healthy subjects is abnormal) 			
Core Urine Monitoring Assessments	
 • Spot UPC ratio • Glycosuria using dipstix • Urine pH using a pH meter 			
Other Screening Tests	
 • HIV • Hepatitis B (HBsAg) • Hepatitis C (Hep C antibody) • FSH and estradiol (as needed in women of non-child bearing potential only) • Alcohol and drug screen (to include at minimum: amphetamines, barbiturates, cocaine, opiates, cannabinoids and benzodiazepines) 			

NOTES :
 
 1. Details of Liver Chemistry Stopping Criteria and Required Actions and Follow-Up Assessments after liver stopping or monitoring event are given in Section 6 and Appendix 2 2. Local urine testing will be standard for the protocol unless serum testing is required by local regulation or ethics committee. 				

7.3.7. High Sensitivity Cardiac Troponin-T (hs-cTnT) Monitoring after a Cardiac Arrhythmia in Part B, or Part C

Baseline hs-cTnT: In Part B and Part C, all subjects will have hs-cTn level for purposes of screening as well as to provide baseline with which to compare, in the event that a subject develops a clinically concerning cardiac arrhythmic event after dosing with GSK3039294.

Subjects should be advised by the local study site to abstain from strenuous exercise (e.g. running or gym work) ≤ 24 hours before a baseline hs-cTn level is taken.

Monitoring of hs-cTnT after an Arrhythmia Event: A blood samples for hs-cTnT will be taken immediately at the time of onset of a cardiac arrhythmia which is deemed by the Investigator to be of clinical concern (see Section 5.4.4), or where there is electrophysiological diagnostic uncertainty.

High-sensitivity cTn levels should be serially repeated (using the same assay) following local troponin monitoring protocols at the study site, and with advice from a cardiologist if this is deemed clinically necessary by the Investigator.

Additional investigations, including but not restricted to serial ECGs and evaluation of cardiac function using echocardiogram and / or cardiac magnetic resonance (CMR) imaging, can be performed at the discretion of the Investigator in consultation with the Medical Monitor and a cardiologist.

7.3.8. Renal Safety Monitoring

All urine studies will be performed in the early morning prior to eating in healthy volunteers (with the exception of the Part B, Day 4 which will be fasting) and patients.

For all Parts of the study, a urine sample will be taken and stored from individual subjects at baseline for each dose level in Part A, at the beginning of week 1 for repeat dosing in Parts B & C, and at the beginning of week 2 in Part B only (see T&E Table).

Core renal parameters will assessed frequently as shown in the T&E Tables.

Table 8 Monitoring of Renal Functions

Subject Group	Core Renal Parameters	Assessments
Healthy Volunteers	Detection of Proteinuria	Spot UPC ratio
Healthy Volunteers & Patients	Assessments of Renal Function	Changes in Serum Creatinine
Healthy Volunteers & Patients	Assessment of Tubule Function	-Glycosuria using dipstix -Urine pH using a pH meter

Subject Group	Core Renal Parameters	Assessments
		-Plasma phosphate levels
Healthy Volunteers & Patients	Assessment of Metabolic Acidosis (if required)	Whenever urine pH is confirmed to be < 6.0 on an average of three readings over 10 minutes from the same urine sample additional assessments e.g. a venous bicarbonate analysis will be initially performed. If this is deemed to be low, an arterial blood gas (ABG) must then be performed to investigate development of metabolic acidosis.

7.3.8.1. Guidance on the Clinical Approach for Suspected Renal Injury

If Renal Injury is Suspected (any subject), additional urine samples will be taken on a prospective basis if biochemical signatures of renal injury are detected at any time during the study. Urine samples will be analysed for biomarkers of renal injury (e.g. KIM-1 and NGAL), as well as for the presence of small molecular proteins (e.g. cystatin C & α 1-microglobulin). The Investigator should liaise with a local nephrologist as regards any additional investigations which may be necessary to confirm either that renal injury has occurred or its nature.

7.4. Pharmacokinetics

7.4.1. Blood Sample Collection

Blood samples for pharmacokinetic (PK) analysis of GSK3039294 (pro-drug), and GSK2315698 (CPHPC) will be collected at the time points indicated. The actual date and time of each blood sample collection will be recorded. The timing of PK samples may be altered and/or PK samples may be obtained at additional time points to ensure thorough PK monitoring.

Part A (Single dose to Healthy Volunteers):

Pre-dose, and 0.25; 0.5; 0.75; 1; 1.5; 2; 3; 4; 5; 6; 8; 10; 12; 16; 24 and 48 hrs post-dose.

Part B – Cohort 3 (7 day repeat dose to Healthy Volunteers):

Study Day	PK sampling timepoint(s)
1	Pre-dose, and 0.5, 1, 2, 3, 4, 6 hrs post-dose
2&3	Pre-dose
4*	Pre-dose, and 0.5; 1; 2; 3; 4; 6 hrs post-dose
5	Pre-dose, and 0.5; 1; 2; 3; 4; 6 hrs post-dose
Follow-up (7 – 14 days post- dose)	Single sample

*Day 4 PK samples will not be collected for sentinel subjects

Part B – Cohort 4a/b (21 day repeat dose to Healthy Volunteers):

Study Day	PK sampling timepoint(s)
1	Pre-dose, and 2hr post-dose (1 st dose of the day only)
2-4	Pre-dose (before 1 st dose of the day only)
5	Pre-dose, and 0.5; 1; 2; 3; 4; 6 hrs post-dose (1 st dose of the day only)
21	Pre-dose, and 0.5; 1; 2; 3; 4; 6; 8 and 12 hrs post-dose (1 st dose; note: 12hr post dose sample to be taken before next dose administration)
Follow-up (7 – 14 days post- dose)	Single sample

If a dose adjustment is required within the 21 day repeat dose period, PK samples will also taken at timepoints indicated below. **Note:** The ‘Dose Day’ relates to the first day of the adjusted dose, and not the study day.

Dose Day	PK sampling timepoint(s)
-1	Pre-dose
1	Pre-dose, and 2hr post-dose (1 st dose of the day only)
2-4	Pre-dose (before 1 st dose of the day only)
5	Pre-dose, and 0.5; 1; 2; 3; 4; 6 hrs post-dose (1 st dose of the day only)
Study Day	
21	Pre-dose, and 0.5; 1; 2; 3; 4; 6; 8 and 12 hrs post-dose (1 st dose; note: 12hr post dose sample to be taken before next dose administration)
Follow-up (7 – 14 days post- dose)	Single sample

Part C (Repeat dose to patients):

Study Day	PK sampling timepoint(s)
1	Pre-dose, and 0.25; 0.5; 0.75; 1; 1.5; 2; 3; 4; 5; 6; 8; 10 and 12 hrs post-dose (note: 12hr post-dose sample to be taken before next dose administration)
2-7	Pre-dose (before 1st dose of the day only)
8-20	Pre-dose (before 1st dose of the day only) on days that a visit is planned
21	Pre-dose, and 0.5; 1; 2; 3; 4; 6; 8 and 12 hrs post-dose (1st dose; note: 12hr post dose sample to be taken before next dose administration)
During Follow-up	1 sample/wk (for first 2 weeks only)

Processing, storage and shipping procedures are provided in the Study Reference Manual (SRM).

7.4.2. Urine Collection

Urine samples for exploratory analysis of GSK3039294, GSK2315698 and possible metabolites will be collected. Details of PK urine sample collection, processing, storage and shipping procedures are provided in the SRM.

7.4.3. Sample Analysis

Pharmacokinetic sample analysis will be performed under the control of PTS-DMPK, GlaxoSmithKline, the details of which will be included in the Study Reference Manual (SRM). Concentrations of GSK3039294 and GSK2315698 will be determined in blood and plasma samples, respectively, using the currently approved bioanalytical methodology. Raw data will be archived at the bioanalytical site (detailed in the SRM).

Once blood / plasma has been analyzed for GSK3039294 and GSK2315698 any remaining blood and plasma extracts may be analyzed for other compound-related metabolites and the results reported under a separate PTS-DMPK, GlaxoSmithKline protocol. The urine samples will be analysed for compound-related material and the results will be reported under a separate DMPK protocol.

7.5. Biomarker(s)/Pharmacodynamic Markers

Blood samples for pharmacodynamic (PD) analysis will be collected at the time points indicated. The actual date and time of each blood sample collection will be recorded. The timing of PD samples may be altered and/or PD samples may be obtained at additional time points to ensure thorough PD monitoring.

Sampling times for SAP samples are given in [Table 9](#) and [Table 10](#). The timing of SAP samples may be altered and/or SAP samples may be obtained at additional time points to ensure thorough SAP monitoring. At each time point samples will be taken from all subjects, however, samples will be analysed on a needs basis.

Blood samples taken in Part B for PD analysis will also be used for the development and validation of a companion diagnostic assay for the analysis of SAP. Blood for this will be taken as an aliquot and stored from the sample that is already being taken for PD analysis.

Table 9 Part B (repeat dose to Healthy Volunteers)

Cohort 3 (7 day repeat dose to Healthy Volunteers):

Study Day	PD sampling timepoint(s)
1	Pre-dose, and 2hr post-dose
2 and 4	Pre-dose
5	Pre-dose, and 0.5; 1; 2; 3; 4; 6 hrs post-dose
7	Pre-dose (before 1 st dose of the day only)
Follow-up (7 – 14 days post-dose)	Single sample

Cohort 4a/b (21 day repeat dose to Healthy Volunteers):

Study Day	PD sampling timepoint(s)
1	Pre-dose, and 2hr post-dose (1 st dose only)
2 and 4	Pre-dose (before 1 st dose of the day only)
5	Pre-dose, and 2hr post-dose (1 st dose of the day only)
Follow-up (7 – 14 days post-dose)	Single sample

If a dose adjustment is required within the 21 day repeat dose period (Cohort 4a/4b), PD samples will also taken at timepoints indicated below. **Note:** The ‘Dose Day’ relates to the first day of the adjusted dose, and not the study day.

Dose Day	PD sampling timepoint(s)
-1	Pre-dose
1	Pre-dose, and 2hr post-dose (1 st dose only)
2-4	Pre-dose (before 1 st dose of the day only)
5	Pre-dose, and 2hr post-dose (1 st dose of the day only)
Study Day	
Follow-up (7 – 14 days post-dose)	Single sample

Table 10 Part C (Repeat dose to Patients)

Study Day	PD sampling timepoint(s)
1	Pre-dose, and; 2; 4; 6; and 12 hrs post-dose (note: 12hr post-dose sample to be taken before next dose administration)
2-7	Pre-dose (before 1 st dose of the day only)
8-20	Pre-dose (before 1 st dose of the day only) on days that a visit is planned
21	Pre-dose, and 0.5; 1; 2; 3; 4; 6; 8 and 12 hrs post-dose (1 st dose; note: 12hr post dose sample to be taken before

Study Day	PD sampling timepoint(s)
	next dose administration)
Safety Follow-up	Single sample
PD Follow-up	1 sample/wk up to 6 weeks

7.6. Genetics

In the event of an unexpected PK profile (i.e. increased or decreased metabolism of GSK3039294) being observed in an individual subject during any Part of the study, germline SNP analysis for recognised esterase-encoded genes which have been previously implicated in the dysfunctional metabolism of other esterase-cleaved prodrugs (e.g. CES-1 in oseltamivir), or genome-wide locus agnostic analysis, will be initiated from the stored blood samples of the affected individual subject(s). In addition, the stored blood samples of the remaining unaffected subjects within that particular part of the study will also undergo SNP analysis. This will facilitate comparative SNP data analysis of the affected subject(s) versus the rest of the study population.

Information regarding genetic research will be included in [Appendix 3](#).

8. DATA MANAGEMENT

- For this study, the data collection tool will be PIMS, a validated computer software program. In all cases, subject initials will be collected in source documentation at the site but will not be transmitted to GSK sponsor team.
- Subject data necessary for analysis and reporting will be entered/transmitted into a validated database or data system.
- Management of clinical data will be performed in accordance with applicable GSK standards and data cleaning procedures to ensure the integrity of the data, e.g., removing errors and inconsistencies in the data.
- Adverse events and concomitant medications terms will be coded using MedDRA (Medical Dictionary for Regulatory Activities) and an internal validated medication dictionary, GSKDrug.
- CRFs (including queries and audit trails) will be retained by GSK. Subject initials will not be transmitted to GSK according to GSK policy.

9. STATISTICAL CONSIDERATIONS AND DATA ANALYSES

9.1. Hypotheses

No formal hypotheses will be tested in this study.

9.2. Sample Size Considerations

9.2.1. Sample Size Assumptions

The sample size for this study is based primarily on feasibility. An assessment of the planned sample size has been based on the level of precision the study would provide

around the estimated true rate of a given safety event and around the estimated SAP depletion levels for a given dose.

9.2.1.1. Safety

Table 11 presents the 95% credible interval for the true event rate of a specific AE, assuming various observed AE rates and a sample size of 6 and 12. Here the credible interval specifies with a fixed probability of 95%, a range of values for the true AE rate after updating some prior position on the true AE rate with the AE data observed during the study. In general, a larger sample size will yield a narrower 95% credible interval.

For example, if we observe one specific adverse event in a single cohort/dosing session with $n=6$, ie an observed AE rate of 17%, then there is a 95% probability that the true AE rate lies between 4 and 58%. This implies that a true AE rate of greater than 58% could occur, though with a 2.5% probability.

Similarly, if we observe one specific adverse event in a single cohort/dosing session with $n=12$, ie an observed AE rate of 8%, then there is a 95% probability that the true AE rate lies between 2 and 36%. This implies that a true AE rate of greater than 36% could occur, though with a 2.5% probability.

Table 11 95% credible intervals for observed adverse event rate

Number of subjects per cohort/dose (n)	Observed number subjects with adverse event	Observed adverse event rate	95% credible interval for adverse event rate, given observed data ¹
6	0	0.00	(0.00, 0.41)
6	1	0.17	(0.04, 0.58)
6	2	0.33	(0.10, 0.71)
12	0	0.00	(0.00, 0.25)
12	1	0.08	(0.02, 0.36)
12	2	0.17	(0.05, 0.45)

(1) derived within a Bayesian framework with a non-informative conjugate prior distribution Beta(1,1)

9.2.1.2. Pharmacodynamics (Plasma SAP)

The standard deviation of log-transformed post-dose plasma SAP depletion levels, based on completed CPHPC studies to date, is assumed to be approximately 0.3 in healthy volunteers and between 0.7 and 0.9 in systemic amyloidosis patients.

With an assumed standard deviation of 0.9 for log-transformed post-dose plasma SAP depletion levels, and 6 subjects, the upper limit of the 95% confidence interval (CI) around the observed geometric mean post-dose plasma SAP level will be 2.57 times the observed geometric mean. Hence, if we observe a geometric mean post-dose plasma SAP level of 2mg/L, then the upper limit of the 95% CI around this observed geometric mean

will be approximately 5.1mg/L. Similarly, if we observe a geometric mean post-dose plasma SAP level of 0.5mg/L, then the upper limit of the 95% CI around this observed geometric mean will be approximately 1.3mg/L.

A small gain in precision is achieved with more than 6 subjects (see Section 9.2.2, Sample Size Sensitivity).

9.2.2. Sample Size Sensitivity

An assessment of sample size sensitivity has been based on the level of precision the study would provide around the estimated true rate of a given safety event and around the estimated SAP depletion levels for a given dose.

9.2.2.1. Safety

Table 12 presents the 95% credible interval for the true event rate of a given AE, assuming various observed AE rates and selected sample sizes between 5 and 20.

Sample sizes of less than 6 per cohort/dosing session were not planned since this would mean, irrespective of the number of events for a given AE in a single cohort/dosing session (i.e. an observed AE rate of $\geq 0\%$) that the upper limit of the 95% credible interval for the true AE rate would range as high as approximately 50% or more.

Sample sizes greater than 12 per cohort/dosing session were not planned since in order to provide significant gains in terms of safety information, the sample size would need to be increased beyond feasibility. For example, with a sample size of 20, if we observe one given adverse event (ie an observed AE rate of 5%) then a 95% credible interval about the true AE rate would still have an upper limit as high as 24%.

Table 12 95% credible intervals for observed adverse event rate

N	Observed number subjects with adverse event	Observed adverse event rate	95% credible interval for adverse event rate, given observed data ¹
5	0	0.00	(0.00, 0.46)
5	1	0.20	(0.04, 0.64)
6	0	0.00	(0.00, 0.41)
6	1	0.17	(0.04, 0.58)
8	0	0.00	(0.00, 0.34)
8	1	0.13	(0.03, 0.48)
10	0	0.00	(0.00, 0.28)
10	1	0.10	(0.02, 0.41)

[figure not shown]
[figure not shown]
N	Observed number subjects with adverse event	Observed adverse event rate	95% credible interval for adverse event rate, given observed data ¹
12	0	0.00	(0.00, 0.25)
12	1	0.08	(0.02, 0.36)
14	0	0.00	(0.00, 0.22)
14	1	0.07	(0.02, 0.32)
16	0	0.00	(0.00, 0.20)
16	1	0.06	(0.01, 0.29)
18	0	0.00	(0.00, 0.18)
18	1	0.06	(0.01, 0.26)
20	0	0.00	(0.00, 0.16)
20	1	0.05	(0.01, 0.24)

(1) derived within a Bayesian framework with a non-informative conjugate prior distribution Beta(1,1)

9.2.2.2. Pharmacodynamics (Plasma SAP)

Figure 5 shows how the precision around the observed geometric mean post-dose plasma SAP levels improves with decreasing standard deviation and increasing sample size (i.e. the factor by which the upper 95% CI is above the observed geometric mean decreases with decreasing standard deviation and increasing sample size).

Given an expected post-dose depletion level for plasma SAP to less than 2mg/L, no significant improvement in precision would be achieved with greater than 6 subjects. Similarly, precision levels across the explored range of standard deviations would not differ significantly.

Figure 6 Impact of standard deviation and sample size on precision

Upper limit of 95% CI = (estimated post-dose plasma SAP) x (precision factor)

Lower limit of 95% CI = (estimated post-dose plasma SAP) / (precision factor)

9.2.3. Sample Size Re-estimation or Adjustment

Additional subjects/cohorts may be enrolled to allow for further evaluation of a given dose or for evaluation of additional dose levels.

9.3. Data Analysis Considerations

9.3.1. Analysis Populations

Safety Population:

This population is defined as all subjects who received at least one dose of study medication. This will be the primary population for assessing safety.

PK Population:

This population is defined as all subjects administered at least one dose of study medication and who have at least one PK sample taken and analysed. This will be the primary population for assessing PK. Subjects will be classified by the actual dose received.

PD Population:

This population is defined as all subjects who received at least one dose of study medication and who also have a baseline measurement and at least one post-treatment PD measure. This will be the primary population for assessing PD. Subjects will be classified by the actual dose received.

PK/PD Population:

This population is defined as all subjects included in both the PK and PD populations. This will be the primary population for PK/PD modelling. Subjects will be classified by the actual dose received.

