Follow-up	At least 7 days and no greater than 14 days after study drug administration. If warranted, additional follow-up visits may be scheduled.
Total Duration	Each cohort is approximately 8 weeks

Figure 2 Study Design for Healthy Volunteer Subjects Single Dose (Cohorts 1 and 2)

All data obtained from this study will be included in the existing PK model established from completed studies with CPHPC [Sahota, 2015] and will inform the dose selection for the next cohort/dosing session.

At the end of this single dose part, all PK data will be analysed (see Section 9.3.2) and reviewed together with all available safety data.

The study drug will be further evaluated in Parts B and C, unless following Part A it is determined that:

- If the safety profile is acceptable however the calculated bioavailability would mean that even following dosing of GSK3039294 at a maximum dose (which does not exceed pre-clinical safety exposure limits), insufficient CPHPC would be generated to be an effective depletor of plasma SAP.

- If the safety profile restricts the maximum well tolerated dose level to one that does not generate sufficient CPHPC to be an effective depleter of plasma SAP.

In this situation the study may be terminated.

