Using the PK/PD model the concentration-time profiles of CPHPC after a single dose of GSK3039294 were simulated, and Cmax and AUC[0-inf] were derived. For a dose of 200 mg, this resulted in a predicted AUC[0-inf] of 14.5 µg.hr/mL (95% CI of 9.5-22.4 µg.hr/mL) and a predicted Cmax of 3.4 µg/mL (95% CI of 2.1-5.0 µg.hr/mL).

The next doses in Part A will be determined based on the data of the preceding dosing sessions. All available PK data will be analysed (see Section 9.3.2.1), and the next dose will be such that the median Cmax will be about 6 µg/mL, and the predicted 95% CI will not exceed preclinical Cmax and AUC limits.

The highest dose in Part A will not exceed pre-clinical safety exposure limits of AUC[0-24] of 250 µg.hr/mL and Cmax of 22.1µg/mL.

Part B

The dose level for Cohort 3 in Part B will be determined based on the PK data obtained in Part A, by analysing all available PK data from Part A and subsequently predicting concentration-time profiles at steady state after repeat dosing. Table 5 shows examples of dose levels and frequencies with predicted AUC[0-24] and C_{max} at steady state, using the PK/PD model that was developed for CPHPC (active molecule) [Sahota, 2015], adjusted for oral absorption and conversion of GSK3039294 into CPHPC. The PK data from Part A will be used to obtain estimates for K_a and F.

Table 5 Example Doses And Predicted Exposures For Part B

Dose	K _a	F	AUC[0-24h] (µg.hr/mL) ^{*)}	C _{max} (µg/mL) ^{*)}
Cohort 3				
300mg OD	1.3	1	23.4 (15.3-35.9)	5.20 (3.32-7.84)
300mg OD	1.3	0.5	11.4 (7.36-18.1)	2.61 (1.72-3.86)
300mg OD	0.6	1	22.8 (14.7-36.2)	3.83 (2.73-5.42)
Cohort 4a (first part)				
300mg BID	1.3	1	45.7 (29.4-72.5)	5.49 (3.75-8.05)
300mg BID	1.3	0.5	22.8 (14.7-36.2)	2.74 (1.87-4.02)
300mg BID	0.6	1	45.7 (29.4-72.5)	4.09 (2.94-5.76)
Cohort 4a (last part)				
600mg BID	1.3	1	91.3 (58.9-145)	11.0 (7.50-16.1)
600mg BID	1.3	0.5	45.7 (29.4-72.5)	5.49 (3.75-8.05)
600mg BID	0.6	1	91.3 (58.9-145)	8.19 (5.88-11.5)

^{*)} Predicted AUC[0-24] and C_{max} at steady state; presented are mean and 95%CI

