The dose levels for subsequent cohorts in Part B will be determined based on the PK data from Part A (single dose), and cohort 3 in Part B (multiple dose). All available PK data will be analysed (see Section 9.3.2.1). The dose levels and dosing frequencies will be chosen such that the predicted 95% CI of C_{max} and AUC at steady state will not exceed preclinical C_{max} and AUC limits (22.1 µg/mL and 250 µg.hr/mL, respectively).

Part C

GSK3039294 will be administered at the predicted optimal clinical dose for 21 days. This dose will be determined using the PK/PD model that was developed for CPHPC (active molecule) [Sahota, 2015]. Using all available PK and plasma SAP (PD) data from Parts A and B, the model will be adjusted for the oral absorption of GSK3039294 and the conversion of GSK3039294 to CPHPC. Plasma concentration-time profiles of CPHPC as well as the plasma SAP time course after repeat dosing with GSK3039294 will be predicted in order to determine the optimal clinical dose and dose frequency. The dose level and frequency will be chosen such that the predicted 95% CI of C_{max} and AUC at steady state will not exceed preclinical C_{max} and AUC limits (22.1 µg/mL and 250 µg.hr/mL, respectively). See Section 9.3.2.1 for further details of the analysis.

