9.3.2. Interim Analysis

Data will be reviewed on an ongoing basis throughout the study by the study team and investigator in order to inform dosing decisions for subsequent dosing sessions, cohorts and study parts. Dose escalation meetings will be held prior to increasing the dose. Key data to inform dosing decisions will include but not be limited to: safety (AEs, clinical laboratory data, vital signs and ECGs), PK (concentrations of GSK2315698, and if possible, GSK3039294 and the intermediate molecule GSK3037412), and plasma SAP levels (Parts B & C only).

In addition to the ongoing review of data throughout the study, at the end of Part B, individual profiles over time will be presented graphically for selected urine and plasma laboratory parameters pertaining to the kidney. Individual profiles will be presented for both single and repeat-dose healthy volunteer data to further inform the evaluation of renal safety and the decision to progress to repeat dosing in systemic amyloidosis patients in Part C.

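### Section 9.3.1's primary population for PK/PD modelling cannot hold subjects with Part A data only, yet 4.2.1 and 4.5 require Part A PK data in that model

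*Protocol*

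**What the plan says.** Section 9.3.1 builds its populations in steps. The PK Population is "all subjects administered at least one dose of study medication and who have at least one PK sample taken and analysed". The PD Population takes dosed subjects "who also have a baseline measurement and at least one post-treatment PD measure". The PK/PD Population is then the overlap: "This population is defined as all subjects included in both the PK and PD populations. This will be the primary population for PK/PD modelling".

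The PD marker is plasma serum amyloid P, and the protocol plans it for the repeat-dose parts only. Section 9.3.2, listing the data that inform dosing, has "plasma SAP levels (Parts B & C only". The sampling tables in 7.5 start at "Table 9 Part B (repeat dose to Healthy Volunteers" and go on to Table 10 for Part C; there is none for Part A. The Part A schedule in 7.1.1 has a PK sampling row and no PD row. Section 3 gives Part A no PD objective.

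The modelling text assumes Part A is in the model. Section 4.2.1, in the Part A description, says: "All data obtained from this study will be included in the existing PK model established from completed studies with CPHPC". Section 4.5 says, for Part B: "The PK data from Part A will be used to obtain estimates for" Ka and F. For the Part C dose it says: "Using all available PK and plasma SAP (PD) data from Parts A and B, the model will be adjusted". Sections 9.3.2.1 and 9.4.2.1 name the tool as the PK/PD model developed for CPHPC, with bioavailability and absorption parameters the only ones estimated and the rest held at reported values.

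**The concern.** The population definition and the modelling plan cannot both be followed. The intersection rule asks for a PD measurement from every subject who enters the model, yet what the model estimates, F and Ka, is informed by concentrations, and Part A supplies concentrations without PD. At the first use of the model, to choose the Cohort 3 dose, nobody meets the definition.

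The model's output matters. Sections 4.5 and 9.3.2.1 use it to predict exposure for Parts B and C, and the 95% intervals of those predictions must stay within the preclinical Cmax and AUC limits. An analyst who applied 9.3.1 literally would leave out data that 4.5 says must be used, including the most densely sampled single-dose profiles in healthy volunteers.

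**Working it through.** The plan states no figure on this point, so there is none to reproduce. The check is set logic followed by a count of scheduled samples.

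**Step 1. Who qualifies at each decision** (two Part A cohorts of 6 from 4.2.1; 6 per Part B cohort from 4.3)

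- Choice of the Cohort 3 dose: PK Population 12, PD Population 0, intersection 0.
- End of Part B (Cohorts 3 and 4a, no Cohort 4b): intersection 6 + 6 = 12. The PK Population is 24 − r, where r is the number of Part A subjects who re-enter in Part B, as 4.3 allows. Part A subjects left out: 12 − r, which is 12 for r = 0, 6 for r = 6 and 0 for r = 12. The protocol does not fix r.

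**Step 2. Scheduled PK samples per subject or profile** (7.4.1)

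- Part A: pre-dose + 16 = 17 per profile.
- Cohort 3: 7 + 2 + 7 + 7 + 1 = 24; a sentinel skips Day 4, so 24 − 7 = 17.
- Cohort 4a: 2 + 3 + 7 + 9 + 1 = 22; a dose adjustment adds 1 + 2 + 3 + 7 = 13.
- Part C: 14 + 6 + 9 + 2 = 31, plus one per visit on Days 8 to 20. The visit count is hard to read from the schedule; I assume 3 or 4, giving 34 or 35.

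**Step 3. Share from Part A, healthy volunteers only, r = 0**

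- Upper case: four Part A dose levels (the planned maximum) and 6 subjects in Cohort 3. Part A is 24 × 17 = 408, Cohort 3 is 6 × 24 = 144, Cohort 4a is 6 × 22 = 132. Share = 408 / 684 = 60%.
- Lower case: three dose levels (the synopsis reports 200, 600 and 1200 mg), 6 subjects per level assumed, and one extra Cohort 3 sentinel, because 6 must complete the food effect and sentinels do not take part in it. Part A is 18 × 17 = 306, Cohort 3 is 144 + 17 = 161. Share = 306 / (306 + 161 + 132) = 306 / 599 = 51%.
- If all six Cohort 4a subjects had a dose adjustment (6 × 13 = 78 more), the shares would fall to 408 / 762 = 54% and 306 / 677 = 45%. Cohort 4b would lower them further.

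**Step 4. Share with Part C (12 patients)**

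- Three dose levels, 34 samples per patient: 12 × 34 = 408; 306 / (599 + 408) = 306 / 1007 = 30%.
- Four dose levels, 35 per patient: 12 × 35 = 420; 408 / (684 + 420) = 408 / 1104 = 37%.

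**Step 5. Samples from 0.25 to 2 h, which inform Ka most directly** (healthy volunteers, 6 in Cohort 3)

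- Part A 24 × 6 = 144, Cohort 3 6 × 9 = 54, Cohort 4a 6 × 7 = 42: 144 / 240 = 60%.
- With 18 Part A profiles: 108 / 204 = 53%.

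**The case against.** The strongest reply is that 9.3.1 excludes nothing. It names a primary population, which is not an exclusive one, and it separately makes the PK Population, which contains Part A, primary for assessing PK. Ka and F are PK parameters. Sections 4.2.1 and 4.5 say which data each modelling step uses, and a sensible analyst would follow those sentences before fitting an empty dataset. Further details are deferred to the reporting and analysis plan, which is not at hand.

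Much of this stands, and it limits what can be claimed. A reader might infer that Part A data will be discarded; the documents do not show that. Other tempting inferences also go too far:

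- That every Part A subject is lost for good. Section 4.3 lets Part A subjects enter Part B, where they could qualify through the sampling done there.
- That dose-linearity after single doses can no longer be checked. Section 9.3.2.1 derives individual Part A Cmax and AUC by non-compartmental analysis, which does not depend on the PK/PD Population.
- That no early absorption samples would remain. Cohorts 3 and 4a sample at 0.5, 1 and 2 h. Part C Day 1 includes 0.25, 0.75 and 1.5 h, though only after the Part C dose is chosen.

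The reply does not remove the contradiction. No sentence assigns the estimation of Ka and F to the PK Population; 9.3.2.1 and 9.4.2.1 place it inside the PK/PD model, for which 9.3.1 names the intersection. Section 10.7.1 mentions any available PD data from Part A dose levels, but the protocol schedules none. A later analysis plan could repair this, but the protocol definition is wrong as it stands; it is not merely silent.

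**Conclusion.** Wrong as written, in a limited form. The primary population that 9.3.1 names for PK/PD modelling is empty when the model is first needed, and afterwards it omits Part A subjects who do not roll over. That contradicts 4.2.1 and 4.5.

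Taken literally, it would remove about half to 60% of planned healthy-volunteer PK samples from the fits, and about 30% (up to 37% with four Part A dose levels) once Part C is counted. These shares assume no roll-over, no Cohort 4a dose adjustment, no Cohort 4b, 6 subjects per cohort or dose level apart from the extra Cohort 3 sentinel in the lower case, and 12 patients in Part C. Departures from the first three assumptions would reduce them.

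No estimate or dose decision is shown to change, and no sample size is affected. The case for acting is that the text gives two incompatible instructions for a model that informs dosing, and the repair is trivial.

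**What to change.** Amend the PK/PD Population entry in 9.3.1 to say that the PK component of the model (Ka and F) uses all PK Population subjects from Parts A, B and C, and that serum amyloid P data are contributed by those subjects in whom it was measured. Keep the intersection as the population for displays of concentration against serum amyloid P. Carry the same wording into the reporting and analysis plan.

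The cost is one sentence in each document. No new samples or visits are needed.
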